Appendix A: Progress Criteria

Project Implementation

Area	Question	Assessment method	Progression criteria	Red Amber Green
1. Fidelity	Are therapy sessions being recorded?	Calculate percentage of therapy sessions delivered that are recorded.	% therapy sessions recorded	≥75%
				74-50%
				<50%
2. Eligibility/ Referral	Do enough referrals received meet the eligibility criteria?	Calculate the percentage of referrals received during months 9-16 ^a of the pilot that were eligible to take part in the study.	% referrals received that met the eligibility criteria	≥75%
				74-50%
				<50%
3. Dosage	Do MBT-PP clients attend enough therapy sessions?	Calculate percentage of clients who attended under six and over six MBT-PP sessions.	i) % clients who were discharged having attended less than six sessions of MBT-PP	≤25%
				26-50%
				>50%

			ii) % clients who were discharged having attended six or more sessions of MBT-PP	
≥75%
 
74-50%
 
<50%

4. Practitioner training	Have MBT-PP therapists received enough training?	Report amount of the five days post-qualification training on MBT-PP received by therapists.	Number of days' training in MBT-PP received by therapists	
All therapists have received full 5 days of training in MBT-PP prior to delivering MBT-PP.
 
One or more therapists have received only 3 or 4 days of training in MBT-PP prior to delivering MBT-PP.
 
One or more therapists have received less than 3 days of training in MBT-PP prior to delivering MBT-PP.

5. Supervision	Do MBT-PP therapists receive enough supervision?	Calculate mean hours of supervision per month for MBT-PP therapists.	Mean hours of supervision per month per MBT-PP therapist (pro-rata if part-time).	
All therapists delivering MBT-PP receive 1.5 hours per month
 
One or more therapists delivering MBT-PP receive less than 1.5 hours, but more than 59 minutes per month
 
One or more therapists delivering MBT-PP receive less than 1 hour per month.

6. Practitioner capacity	Do MBT-PP therapists have the capacity to work with clients as intended?	Calculate percentage of families (or individual parents, if parents are attending therapy separately) that are contacted by the therapist within 2 weeks of being allocated to a therapist.	% families contacted by a therapist within 2 weeks of being allocated a therapist	
≥75%
 
74-50%
 
<50%

^a First two months of referrals not included while referrers learn pathway. Project then delayed by set up difficulties, leading to a 4 month extension, hence percentage of eligible referrals to be counted from month 9-16.

Evaluation Measurement

Area	Question	Assessment method	Progression criteria	Red Amber Green
7. Overall recruitment to evaluation.	Have enough families been recruited? Is the project on track to meet the recruitment needed for the efficacy study?	Comparison of actual vs. required recruitment.	i) In months 3-12, 140 families are expected to have been recruited and randomised.	≥75% of target (105 families)
				74-50% of target (70-104 families)
				<50% of target (<69 families)
			ii) % of recruited families where both parents are participating	≥80% of recruited families (112 families)
				55-79% of recruited families (77-111 families)
				<55% of recruited families (<77 families)
8. Attrition from MBT-PP.	Have enough families that started MBT-PP completed the treatment protocol?	Therapist report of whether families were discharged before completing the treatment protocol i.e., before reaching the 'ending and signposting phase' of treatment.	% families who attended session 1 who were discharged before completing treatment protocol	<30% of families who attended session 1
				30-50%
				≥50%
9. Attrition from the evaluation.	Have enough parents and CYP completed the post-treatment outcome measures?	Comparison of actual vs. expected attrition from the evaluation (completing post-treatment outcome measures).	i) Attrition of Parent 1 (provider of primary outcome measure) across study arms.	≤10% of those recruited and randomised
				11-30%
				>30%
	Does attrition differ systematically between study arms?		ii) Percentage of Parent 1s who were lost from evaluation who were in MBT-PP condition (aiming for approx. half).	45-55%
				35-44% or 56-65%
				<35% or >65%

			iii) Attrition of Parent 2s (who completed baseline measures) across study arms.	
≤10% of those recruited and randomised
 
11-30%
 
>30%

			iv) Percentage of Parent 2s who were lost from evaluation who were in MBT-PP condition (aiming for approx. half).	
45-55%
 
35-44% or 56-65%
 
<35% or >65%

			v) Attrition of CYP (who completed baseline measures) across study arms.	
≤10%
 
11-30%
 
>30%

			vi) Percentage of CYP who were lost from evaluation who were in MBT-PP condition (aiming for approx. half).	
45-55%
 
35-44% or 56-65%
 
<35% or >65%

Measurement and findings

Area	Question	Assessment method	Progression criteria	Red Amber Green
10. Acceptability/		Calculate proportions of participants allocated to each condition.	% participants allocated to MBT-PP	
45-55%
 
35-44% or 56-65%

feasibility of randomisation.	Did randomisation work? Were there any problems?	Reflections on randomisation process from SHU, TR and LAs.	Degree of problems reported with randomisation process.	<35% or >65%
				No problems.
				Minor problems, refinements to processes needed.
				Significant problems, major changes to processes needed.
11. Data quality.	Is the baseline and post-treatment primary outcome measure data of high quality?	Calculate amount of missing data within SDQ responses that have been collected	% missing data within the 25 SDQ items completed by parents at baseline and post-treatment	≤10%
				10-30%
				>30%
12. Effective use of core measures.	Is there an effective mechanism in place to collect the outcome measures?	Report mechanisms for collecting outcome measures.	Mechanisms in place to collect outcome measures from parents and CYP.	A Gateway Lead is in post in each LA to liaise with evaluator for the completion of baseline, post-treatment and follow-up outcome measures.
				There is not a Gateway Lead currently working in each LA, but alternative arrangements to support data collection have been/are being made where necessary.
				There is not a mechanism in place to support data collection in each LA.

youthendowmentfund.org.uk

[contact]

[@YouthEndowFund](https://twitter.com/YouthEndowFund)

The Youth Endowment Fund Charitable Trust

Registered Charity Number: 1185413

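### Three progression cut-offs in Appendix A are wrong at a single edge value: the red count in criterion 7i, 50% in criterion 8 and 10% in criterion 11

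*Protocol*

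**What the plan says.** Appendix A (Progress Criteria) sets bands for each pilot criterion. The Internal Pilot Study section says that an amber or red rating means mitigation is needed before the trial moves on. I read the three bands in each cell, in order, as green, amber and red.

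- **Criterion 7i (recruitment).** The target is: "In months 3-12, 140 families are expected to have been recruited and randomised". The bands are "≥75% of target (105 families", "74-50% of target (70-104 families" and "<50% of target (<69 families".
- **Criterion 7ii (both parents taking part).** The lowest band is "<55% of recruited families (<77 families", and amber starts at 77.
- **Criterion 8 (attrition from therapy).** The measure is the percentage of "families who attended session 1 who were discharged before completing treatment protocol". The bands are <30%, 30-50% and ≥50%.
- **Criterion 11 (data quality).** The measure is the percentage of "missing data within the 25 SDQ items completed by parents at baseline and post-treatment". The bands are ≤10%, 10-30% and >30%.
- **Criterion 3 (dosage).** The assessment-method column reads: "Calculate percentage of clients who attended under six and over six MBT-PP sessions". The two rated statements in the same row use fewer than six and six or more.

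I find no statement in the available text of either document on how a value at an edge is rated, or on whether percentages are rounded first.

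**The concern.** Progression bands are fixed in advance so that the rating follows from the data. If a value belongs to two bands, or its printed count and printed percentage disagree, someone must choose the rating after seeing the result. That matters most at the green/amber edge, because green needs no mitigation and amber does. Criterion 11 has its overlap exactly there.

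**Working it through.** **Inputs.** The target of 140 families and all bands come from Protocol Appendix A.

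**Criterion 7i: reproduce the printed counts.** Count = percentage × 140.

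- Green edge: 0.75 × 140 = 105. Matches the printed 105.
- Amber lower edge: 0.50 × 140 = 70. Matches the printed 70.
- Red edge: below 0.50 × 140 means below 70, that is 69 or fewer. The printed count is below 69. Does not match.

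| Families | % of 140 | Band by count | Band by percentage |
|---|---|---|---|
| 68 | 48.6 | red | red |
| 69 | 49.3 | none | red |
| 70 | 50.0 | amber | amber |
| 104 | 74.3 | amber | between 74 and 75 |
| 105 | 75.0 | green | green |

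The next row of the table gets the same arithmetic right: 0.55 × 140 = 77, red is below 77 and amber starts at 77. The 69 in 7i therefore looks like a slip for 70, not a convention.

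**Criterion 8: test values around the edge.**

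- 49.9%: amber only.
- 50%: satisfies 30-50% and also ≥50%, so amber and red.
- 50.1%: red only.

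**Criterion 11: test values around the edge.**

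- 9.9%: green only.
- 10%: satisfies ≤10% and also 10-30%, so green and amber.
- 10.1%: amber only.

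**Comparison inside the same appendix.** Criterion 9 (i, iii and v) uses ≤10% then 11-30%, and criterion 3i uses 26-50% then >50%. Neither overlaps, so the overlaps in 8 and 11 are not the table's general style.

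**Would rounding cure the overlaps?** No. If results are rounded to whole percentages, everything from 9.5% to just under 10.5% becomes 10%, and everything from 49.5% to just under 50.5% becomes 50%. The double-rated range then gets wider.

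**The case against.** Several stronger readings are tempting, and the documents do not support them.

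- **That 69 families cannot be rated.** The band is defined as below 50% of target, with the count as a gloss in brackets. 69/140 = 49.3% is below 50%, and no other band claims 69, so it is red. Only the count is wrong.
- **That criterion 3 leaves clients with exactly six sessions unclassified.** The loose wording is confined to the method column. The rated statements in that row cover every value, and the SAP Compliance section likewise uses six or more.
- **That the whole-number bands leave gaps which are likely to be hit.** In criterion 7 the printed counts close the gaps: 104/140 = 74.3% and 111/140 = 79.3% are both listed as amber. For attrition in criterion 9i, 15 losses out of 140 is 10.7%, between the printed 10% and 11%. With true attrition of 10%, exactly 15 losses would have binomial probability 0.104. But that takes 140 as the denominator. The Timeline limits pilot post-intervention data to March-December referrals, and the SAP sample size section gives 90 families at pilot. With 90, 9 losses is 10.0% and 10 losses is 11.1%, so no count falls between the bands. What remains is that a rounding rule is missing.
- **That the progression decision turns on these edges.** In criterion 8 both amber and red require mitigation. In criterion 11 the percentage is taken over 25 items, many parents and two time points, so an unrounded result of exactly 10% is unlikely. The Timeline has the funder deciding after a pilot report, and describes no automatic rule.

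There is also a fair point on timing. The Timeline puts the decision in late June 2024, and the SAP dated 17/01/25 already uses pilot data and plans for stage 2. If its 90 families is the count for 7i, which is not certain because that criterion covers months 3-12, then 90/140 = 64.3% is plainly amber and the faulty edge did not arise.

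None of this removes the three slips themselves.

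**Conclusion.** Wrong as written; minor. The red count in 7i contradicts its own percentage by one family, and criteria 8 and 11 each give one value two ratings. The accurate statement is that a result of exactly 50% in criterion 8 or exactly 10% in criterion 11 cannot be rated uniquely. It would go too far to say that pilot results at thresholds cannot be rated. Criterion 11 carries slightly more weight than the other two, because its overlap decides whether mitigation is required. The finding assumes only the green, amber, red order of the bands and the 140-family target printed in the table.

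**What to change.** In Appendix A:

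1. Criterion 7i: change the red count to <70 families.
2. Criterion 8: the authors should assign 50% to one band only. The documents do not settle which.
3. Criterion 11: make amber >10% to 30%, in line with the ≤10% green band in criterion 9.
4. Add one line saying whether percentages are rounded before they are rated, and to what precision.
5. Optional: align the method wording in criterion 3 with its rated statements (fewer than six; six or more).

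The cost is wording only, with no change to data or analysis. If the progression decision has already been taken, do not re-cut the bands. State in the report which rule was applied and whether any result fell on an edge.

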The trial design is simple in structure, and aims to compare the effects of MBT-PP against TAU on a range of measures. Participants (parents and children) will complete baseline measures before being randomised to receive either MBT-PP or TAU. After 16 weeks (when MBT-PP is complete) the baseline measures will be repeated (post-intervention). Three months after the end of the intervention (3-month follow-up), measures will be repeated a final time. The inclusion of a number of secondary measures enables the trial not only to answer the question of whether MBT-PP is effective in improving child outcomes as measured by the SDQ, but also to identify the mechanisms of action for these positive effects.

A concurrent implementation and process evaluation (IPE) will run throughout both the pilot and efficacy phases. The IPE will be designed to generate insights into the challenges associated with formulating the referral pathways, as well as the processes associated with the delivery of the intervention.

Intervention

MBT-PP

Tavistock Relationships' Mentalization Based Therapy – Parenting Under Pressure (MBT-PP) is a 10-week intervention for parents which is suitable for separated parents or intact couples. The 10 sessions across 16 weeks include 2 assessment sessions and 8 sessions that begin by introducing the skills and behaviours necessary for mentalizing: the capacity to hold others in mind when emotionally aroused and to avoid a swift eruption of conflict. The subsequent sessions build on this ability to think about parents' own feelings and beliefs, those of their partner, and the needs of their children, ending with a focus on how to maintain the achievements made.

Who: The target population for this intervention is parents of children experiencing high levels of persistent and unresolved conflict. The intervention is delivered to parents only – there is no direct therapeutic work with children. This evaluation focuses specifically on parents of children aged 8-14 years. Recruitment will be via referrals from Early Help in 3 local authorities: Dorset Council, Bournemouth, Christchurch, and Poole (BCP) Council, and Bristol City Council.

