What: The intervention consists of MBT-PP, delivered online. After an initial assessment period, which consists of individual sessions for each parent with the therapist, both parents will take part in joint sessions, online, with the therapist. If only one parent is willing to take part, the therapist will work with that parent on their own. MBT-PP is delivered by MBT-PP practitioners, all of whom are qualified therapists, counsellors, family therapists, or child and adult psychotherapists, accredited and registered with their relevant professional bodies (BACP, UKCP, AFT etc.) and compliant with the requirements of these professional bodies, including ethical standards and professional supervision. Treatment fidelity is supported through fortnightly group supervision, offered by MBT-PP Supervisors who have received additional training. Supervisors attempt to ensure adherence to, and prevent departure from the manualised intervention. This allows TR to maintain fidelity, clinical oversight, manage risk and develop practitioners' skills further. Supervisors' work, in turn, is overseen by monthly supervision of supervisors, delivered by the most experienced MBT-PP leaders.

How much: The intervention consists of 10 sessions delivered over (approximately) 16 weeks. The first 2 sessions last up to 75 minutes, and sessions 3-7 inclusive last 60 minutes. Sessions are usually delivered weekly or fortnightly, allowing participants some scheduling flexibility. Sessions are delivered online, via secure Zoom or Teams calls, depending on client preference.

Treatment as usual (TAU)

Because of the aforementioned under-developed pathways for tackling IPC in LAs, it is likely that true TAU, that is, what would occur in the absence of this trial, will vary extremely widely. Because of the nature of family support provision by LAs, understanding the precise nature and content of all the possible interventions is not possible. For example, we would not be able to appraise the intensity or content of family support worker visits to a family home, in which the impact of IPC on the children may either become a focal point, or be tackled much more indirectly, if at all. In this scenario it would be very difficult to understand whether the active ingredients of MBT-PP are in fact unique to the intervention received in the MBT-PP arm.

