March 2023-April 2024	
Pilot baseline data collection.
 
Referrals that come in from March-Dec will have post-intervention data included in the pilot study primary outcome analysis. Referrals coming in Jan-April will have baseline data only included in the analyses to address the aims of the pilot study regarding recruitment and acceptability.
	AM & EC, with input from rest of Evaluation Team

May-June 2024
	
Transition.
 
Evaluators prepare draft report on pilot, for submission end of May. YEF make progression decision by late June.
	
SD, JR, with input from rest of Evaluation Team.
 
AM & EC, with input from rest of Evaluation Team

July 2024-Dec 2024
	
Reflect on feedback from report. Make any alterations necessary to procedures.
 
Efficacy baseline data collection.
 
IPE data collection.
	
AM & EC, with input from rest of Evaluation Team

Jan-April 2025
	
Efficacy post-intervention data collection
 
IPE data collection.
	
AM & EC, with input from rest of Evaluation Team

May-Dec 2025
	
Complete 3 month follow up data collection.
 
Complete IPE data collection.
 
Analysis and reporting.
	
AM & EC, with input from rest of Evaluation Team.
 
SD, JR, with input from rest of Evaluation Team.

References

- Adamsons, K., & Pasley, K. (2006). Coparenting following divorce and relationship dissolution. In M. Fine & J. Harvey (Eds.), *Handbook of Divorce and Relationship Dissolution*, pp. 241-262. Mahwah, NJ: Lawrence Erlbaum
- Altman, D.G. & Bland, M.J. (2005) Statistics Notes: Treatment allocation by minimisation. *BMJ* 330 p843
- Arnold, D. S., O'leary, S. G., Wolff, L. S., & Acker, M. M. (1993). The Parenting Scale: a measure of dysfunctional parenting in discipline situations. *Psychological Assessment*, 5(2), 137. <https://doi.org/10.1037/1040-3590.5.2.137>

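### Progression criterion 8 counts families still in therapy as retained, so pilot dropout reads low; criterion 3 has a related denominator problem

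*Protocol*

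**What the plan says.** **Criterion 8** (protocol, Appendix A, Evaluation Measurement) uses therapist report to give the percentage of "families who attended session 1 who were discharged before completing treatment protocol". Green is below 30%, amber 30-50%, red 50% or more.

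**Criterion 3** (Appendix A, Project Implementation) has two parts. Part i is the percentage of "clients who were discharged having attended less than six sessions of MBT-PP", green at 25% or less. Part ii is the percentage discharged after six or more sessions, green at 75% or more. The cut-points are complementary, which implies that discharged clients are the denominator, but none is stated.

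**Criterion 9** i and iii set green at "≤10% of those recruited and randomised".

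None of these three has a referral window. Criteria 2 (months 9-16) and 7 i (months 3-12) do.

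**Timing.** On treatment length the protocol says: "The intervention consists of 10 sessions delivered over (approximately) 16 weeks". The Timeline puts pilot baseline collection in "March 2023-April 2024", the draft pilot report at the end of May 2024 and the funder's decision in late June. It also splits the pilot referrals. For the first group: "Referrals that come in from March-Dec will have post-intervention data included in the pilot study primary outcome analysis". For the second: "Referrals coming in Jan-April will have baseline data only included in the analyses to address the aims of the pilot study", namely those on recruitment and acceptability.

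**The concern.** Criterion 8 fixes its own denominator, and that denominator includes families who have had no chance to finish. A family at its third session when the data are cut is in the denominator but not in the numerator, even if it leaves a fortnight later. With rolling recruitment, the shortfall depends on how many families started late, not on how well families are retained.

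Criterion 3 has a different problem. It counts discharged clients, and early leavers are discharged weeks before completers who started on the same day. Among recent starters, the discharged are therefore mostly early leavers.

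The Internal Pilot Study section lists signs of problematic attrition among the pilot aims and says that the aims inform the progression criteria, with amber or red requiring mitigation before progression. A colour that is too favourable on criterion 8 could let a retention problem through without it. Version 3.1 of the protocol moved the window of criterion 2 because of the pilot extension, but gave criteria 3 and 8 no window.

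**Working it through.** **The plan's own figures.** The only computed counts in these tables are in criterion 7, and they reproduce: 140 × 0.75 = 105, 140 × 0.50 = 70, 140 × 0.80 = 112, 140 × 0.55 = 77. Criteria 3, 8 and 9 give cut-points only.

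**Inputs from the documents.** Fourteen months of pilot recruitment (60.9 weeks), a 16-week course of 10 sessions, and a report at the end of May 2024.

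**Assumptions not in the documents.** Accrual is even, or rises linearly from zero (ramped). Session 1 is 3 weeks after referral. Dropout is spread evenly over the 16 weeks. Fewer than six of ten sessions means leaving in the first 60% of the course. The data cut is at the end of April (week 60.9) or the end of May (week 65.2).

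**Criterion 8.** Let *e* be the weeks from session 1 to the cut and *d* the true dropout. The observed value is *d* × A, where A is the mean of min(*e*/16, 1) over families that have started.

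- Even accrual, end-April cut: starters span 60.9 − 3 = 57.9 weeks. A = (41.9 + 16/2)/57.9 = 0.862.
- Ramped accrual, end-April cut: A = (41.9/57.9)² + 2 × (57.9 × 16²/2 − 16³/3)/(16 × 57.9²) = 0.524 + 0.225 = 0.749.

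**Criterion 3 i.** With discharged clients as the denominator, the observed value is *d*S/(*d*A + (1 − *d*)B). S is the mean of min(*e*/16, 0.6) and B is the share of starters with *e* ≥ 16. With all clients as the denominator it is *d*S. A true dropout of 35% gives a true short dosage of 0.6 × 35% = 21%. For even accrual and an end-April cut: 0.35 × 0.5502/(0.35 × 0.8618 + 0.65 × 0.7235) = 0.1926/0.7719 = 24.9%.

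| Accrual, cut | A | Crit. 8, true 33% | Crit. 8, true 50% | Crit. 3 i, true 21%, discharged | Crit. 3 i, true 21%, all clients |
|---|---|---|---|---|---|
| Even, end April | 0.8618 | 28% | 43% | 24.9% | 19.3% |
| Even, end May | 0.8898 | 29% | 44% | 24.6% | 19.8% |
| Ramped, end April | 0.7490 | 25% | 37% | 29.4% | 17.7% |
| Ramped, end May | 0.7973 | 26% | 40% | 28.5% | 18.7% |

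**Where criterion 8 changes colour.** It reads green whenever *d* × A < 30%, that is *d* < 30%/A. The limit is 33.7% or 34.8% with even accrual and 37.6% or 40.1% with ramped accrual. A true dropout between 30% and that limit is amber but reads green.

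**Same model, March-December 2023 referrals only.** Criterion 8 returns 32.9% to 33.0% for a true 33%, and 49.8% to 50.0% for a true 50%. Criterion 3 i among discharged clients returns 21.0% to 22.1% for a true 21%. The small remainder is a late-December tail: a family referred on 31 December with a 3-week lag finishes on 12 May 2024 (19 weeks), after an end-April cut but before the end of May.

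**The case against.** The strongest reply is that the Timeline already sets the cohort. January-April 2024 referrals supply baseline data only, and with month 1 as January 2023 the March-December group is months 3-12, the window in which criterion 7 expects 140 families.

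For criterion 9 this largely succeeds. A reader might infer that evaluation attrition is inflated, since with even accrual 16/60.9 = 26% of randomised families would not be 16 weeks out at the end of April. That requires scoring a questionnaire not yet due as a loss. No passage says to do so. The baseline-only rule argues against it, as does criterion 9's own reference to participants lost from the evaluation.

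For criteria 3 and 8 it does not succeed. The Timeline rule is written for questionnaire data and the primary outcome analysis. It does not mention session or discharge records, and Appendix A does not refer to it.

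A second reply is that the size depends on assumptions. That stands. With even accrual, a true 35% reads 30% to 31% and stays amber, and a true 21% on criterion 3 i stays just inside green; only ramped accrual takes these two over a boundary.

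A third is that amber or red calls for mitigation, not stopping, and that the decision was due in June 2024, before the SAP version of 17/01/25. That also stands. It limits what a correction can now change.

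**Conclusion.** The point holds for criterion 8. Its stated denominator biases dropout downwards under rolling recruitment, by a factor of about 0.75 to 0.89 in the scenarios checked. The direction follows from the wording, provided some families are mid-course at the cut and some of them later leave. The size and the colour changes are conditional on the assumed accrual, lag, dropout pattern and cut date.

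For criterion 3 the point holds only on its natural reading. With discharged clients as the denominator, short dosage is overstated; with all clients, 3 i is understated (a true 21% reads about 18% to 20%). It would be wrong to say that criterion 3 counts families still in therapy, or that it overstates short dosage whatever the denominator.

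Criterion 9 needs a clarification and is not shown to be biased. This is a flaw in the pilot decision rule and does not bear on the type I error, power or primary analysis of the trial.

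**What to change.** In Appendix A, calculate criteria 3 and 8 on the March-December 2023 referrals only. Classify each of those families as completed, left early or still in therapy, with the last group shown separately so that a late-December tail is visible. Report session and discharge data for the January-April 2024 referrals descriptively. Add a cross-reference to the Timeline that applies the same cohort to criterion 9.

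If the progression decision has already been taken, apply the same rule where the pilot results are documented, and state the denominators that were used.

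No new data are needed. The cost is precision: with even accrual the cohort is 10/14 = 71% of pilot referrals, so standard errors of these percentages rise by about √(14/10) = 1.18. With ramped accrual it is (10/14)² = 51%, and the factor is 14/10 = 1.4.
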